2.1.3 Data Transformations

2.2 Analysis Populations

The statistical analyses will be performed based on the following subject populations.

2.2.1 Intent-to-treat Efficacy Population

The Intent-to-treat (ITT) population includes all subjects who are randomized and dispensed (i.e., administered) the investigational product, and will be analyzed according to the randomization scheme. All efficacy variables will be analyzed based on the ITT population.

2.2.2 Per-Protocol Efficacy Population

The Per-Protocol (PP) population includes all ITT subjects who have no protocol deviations considered to have a substantial impact on the primary efficacy outcome, and will be analyzed according to the randomization scheme. If the PP population contains less than 90% of the subjects in the ITT, a sensitivity analysis of the primary efficacy endpoint will be performed based on the PP population.

2.2.3 Safety Population

The safety population includes all subjects who were administered the investigational product, and will be analyzed according to as-treated principle. All safety data will be summarized descriptively based on the safety population.

2.3 Study Subjects

2.3.1 Subject Disposition

The number of subjects screened will be shown in total and by study center.

The number of subjects in each study population (i.e., ITT, PP, and Safety) will be summarized by study center and in total (by treatment group and overall).

The disposition of subjects will be presented by treatment group, and in total, including numbers of subjects who were:

GALDERMA Title 43USD1804 Statistical analysis plan

- Randomized,
- Completed,
- Withdrawn (including primary reason for withdrawal).

These numbers will also be presented by study center. The number of completed and withdrawn subjects will also be presented by visit.

2.3.2 Protocol Deviations

Subjects with any protocol deviations will be summarized by study center and in total (by treatment group and overall).

Depending on the seriousness of the deviation, a subject might be excluded from the PP population, which shall be documented prior to database lock. Since the PP population will be used for the primary analysis at Month 1 only, the focus will be on major deviations occurring before and on the Month 1 visit which are considered to have a substantial impact on the primary efficacy outcome. Reasons for exclusion from the PP population will be presented by treatment group and overall.

2.3.3 Demographic Characteristics

Subject demographic data will be summarized for the ITT population by treatment group and overall. Age and body mass index will be analyzed as continuous variables. Gender, race, ethnicity, Fitzpatrick skin type, childbearing potential, and toxin naïve status will be analyzed as categorical variables.

2.3.4 Medical History, Medications, and Procedures

All summaries will be done for the ITT population by treatment group and overall.

Prior and concomitant medications will be coded using the World Health Organization Drug Dictionary (WHODD). Medical history, allergen history (food and drug), and prior and concomitant procedures/non-pharmacological treatments will be coded according to MedDRA.

Prior medications/procedures are the medications/procedures with stop dates prior to study treatment. Medications/procedures started or continuing after the study treatment will be considered concomitant.

The number and percent of subjects reporting medical history, allergen history, cosmetic treatments/procedures, and prior and concomitant procedures/non-pharmacological treatments will be summarized by system organ class (SOC) and Preferred Term (PT).

The number and percent of subjects reporting prior and concomitant medications will be summarized separately, by WHODD Anatomical Therapeutic Chemical (ATC) Class Level 3 (if Level 3 is not available, will use the highest class available) and WHODD generic name.

2.4 Efficacy Analysis

2.4.1 Datasets Analyzed

All efficacy variables will be analyzed based on the ITT population. A sensitivity analysis of the primary efficacy endpoint will be performed based on the PP population, if the PP population contains less than 90% of the subjects in the ITT. Summary statistics will be computed for each

Doc id 43USD1804 Statistical analysis plan -GALDERMA

efficacy endpoint using the Observed Cases (OC) with no imputation for missing data. Inferential statistical analyses will account for missing data as appropriate (SAP Section 2.4.2 below).

[figure not shown]
2.4.2 Handling of Missing Data

[figure not shown]
The OC will be used for all secondary efficacy analyses, safety analyses, as well as the exploratory analyses. The primary ITT analysis will be performed using the baseline observation carried forward (BOCF). A sensitivity analysis of the primary endpoint will be performed using multiple imputation (MI) for missing values. If deemed necessary, any analyses may be repeated using OC, BOCF, or MI as appropriate.

Multiple Imputation

The imputation using MI will assume Missing Completely at Random (MAR). The MI procedure of the SAS® system will be used to generate five sets of data with missing values imputed from observed data. It is expected that the pattern of missing data will be monotonic, with slight deviations being corrected by the Markov Chain Monte Carlo (MCMC) method of the MI procedure. Linear regression will be employed to model the missing ILA scores, with the following covariates included in the imputation model: treatment and non-missing data from earlier visits than Month 1 The imputed datasets will be analyzed using the methodology described for the primary analysis. The results from the analysis of the multiple imputed datasets will be combined by the MIANALYZE procedure of the SAS® system.

Primary Efficacy Analysis

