11.6.3 Archives68

11.7 Insurance68

[REDACTED]
[REDACTED]

12 LITERATURE REFERENCE LIST.....70

13 Appendices.....71

[REDACTED]
[REDACTED]
[REDACTED]
[REDACTED]
[REDACTED]

Effective date: 2019-08-09 13:21

[REDACTED]
[REDACTED]

List of Tables

[REDACTED]
[REDACTED]
[REDACTED]

List of Figures

[REDACTED]

Effective

Version: 6.0

Effective date: 2019-08-09 13:21

Effective

SYNOPSIS	
Clinical Study Title: A Multicenter, Randomized, Dose-Ranging Double-Blind, Placebo-Controlled Study to Evaluate Safety and Efficacy of AbobotulinumtoxinA for the Treatment of Moderate to Severe Platysmal Bands	
Short Title: abobotulinumtoxinA for the treatment of moderate to severe platysmal bands	
Clinical Study Population:	Male and female subjects, 18 to 65 years of age with moderate to severe platysmal bands
Clinical Study Design:	
This is a phase 2, multicenter, randomized, dose-ranging, double-blind, placebo-controlled study in the US to assess the efficacy, safety, and duration of response of abobotulinumtoxinA for the treatment of moderate to severe platysmal bands.
 
[REDACTED]
 
[REDACTED]
 
[REDACTED]
 
[REDACTED]
 
[REDACTED]
 
[REDACTED]
 
[REDACTED]
 
[REDACTED]
 
[REDACTED]
 
[REDACTED]
 
[REDACTED]

[REDACTED]	[REDACTED]
Number of Clinical Study Centers (Planned):	Up to 8 centers
Region(s) / Country(ies) Involved (Planned):	US
Clinical Study Duration:	
The planned duration of recruitment for each treatment group (from FSFV to LSFV) is approximately 4 months.
 
[REDACTED]

Duration of Subject Participation:	[REDACTED]

Effective date: 2019-08-09 13:21

Effective

Version: 6.0

SYNOPSIS	
Clinical Study Title: A Multicenter, Randomized, Dose-Ranging Double-Blind, Placebo-Controlled Study to Evaluate Safety and Efficacy of AbobotulinumtoxinA for the Treatment of Moderate to Severe Platysmal Bands	

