9.1.2.4 Imputation of Missing Data

The Observed Cases (OC) will be used for all secondary efficacy analyses, safety analyses as well as the exploratory analyses. The primary ITT analysis will be performed using the baseline observation carried forward (BOCF) method for missing values. A sensitivity analysis of the primary endpoint will be performed using multiple imputation (MI) [REDACTED]

[REDACTED]

Version: 6.0

Effective date: 2019-08-09 13:21

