9.1.3 Data Presentation and Graphics

[REDACTED]

Subject disposition, completion and discontinuation by study visit, protocol deviations, demographics and baseline characteristics, medical history, medical and surgical procedures, prior and concomitant medications, will be summarized by treatment group.

All efficacy variables will be summarized by treatment at each visit. [REDACTED]

[REDACTED]

[REDACTED]

[REDACTED]

[REDACTED]

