1.1.1 Study Design

This is a phase 2, multicenter, randomized, dose-ranging, double-blind, placebo-controlled, United States (US) study to assess the efficacy, safety, and duration of response of abobotulinumtoxinA for the treatment of moderate to severe platysmal bands.

After undergoing a screening visit, enrolled subjects will receive a single treatment of abobotulinumtoxinA or placebo at baseline. The planned clinical study duration (from first subject first visit to last subject last visit) is approximately 21.5 months.

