2.1.2 Reporting Conventions

The formats for the tables, listings, and figures described in this SAP will be provided in a companion document. Changes to the formats of these reports that are decided after the finalization of the SAP will not require an amendment. In addition, any additional supportive or exploratory analyses requested after SAP approval will not require amendment of the SAP. These additional analyses will be described in the CSR.

All study data from the eCRFs as well as derived variables will be provided in subject data listings. An indication of specific listings for each data type will not be indicated in the text of subsequent SAP sections. Data listings supplied as part of the CSR will be sorted by treatment group, study center number concatenated with subject number, assessment dates, and/or time point.

The following conventions will be applied to all data presentations and analyses:

- Placebo-treated subjects will be pooled together in summary tables and for analyses.
- Treatment groups to be summarized include abobotulinumtoxinA and pooled placebo.
- Quantitative variables will generally be summarized by the number of subjects, mean, standard deviation, median, minimum, and maximum. Unless otherwise specified, the minimum and maximum values will be displayed to the same number of decimal places as the raw data, the mean and median will be presented to one extra decimal place compared to

GALDERMA

Title

43USD1804 Statistical analysis plan -

the raw data, and the standard deviation will be displayed to two extra decimal places compared to the raw data.

- Categorical variables will be summarized by the number and percentage of subjects within each category. Unless otherwise specified, the percentage will be presented in parentheses to one decimal place. Frequency and percentage values of 0 will be presented as '0' rather than '0 (0)'.
- All summary tables will include the analysis population sample size (i.e., number of subjects) in each treatment group.
- Date variables will be formatted as DDMMMYYYY for presentation.

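### Does analysing secondary and exploratory efficacy on observed cases, with no mandatory missing-data sensitivity analysis after Month 1, undermine the duration-of-response results?

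*SAP*

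**What the plan says.** SAP 2.4.2 (Handling of Missing Data) sets the rule: "The OC will be used for all secondary efficacy analyses, safety analyses, as well as the exploratory analyses". Protocol 9.1.2.4 agrees: "The Observed Cases (OC) will be used for all secondary efficacy analyses, safety analyses as well as the exploratory analyses". For the Month 1 primary, both documents use baseline observation carried forward (BOCF), with multiple imputation (MI) as the sensitivity analysis. The visible covariate list of the MI model is "treatment and non-missing data from earlier visits than Month 1". For everything else SAP 2.4.2 adds: "If deemed necessary, any analyses may be repeated using OC, BOCF, or MI as appropriate".

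SAP 1.1.1 describes a "study to assess the efficacy, safety, and duration of response of abobotulinumtoxinA", and the design entry of the protocol synopsis says the same.

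The planned output also bears on the point:

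- Protocol 9.1.3: "All efficacy variables will be summarized by treatment at each visit". The same section plans completion and discontinuation by study visit and treatment group.
- SAP 2.3.1: completed and withdrawn subjects are also shown by visit.
- SAP 2.1.2: "Categorical variables will be summarized by the number and percentage of subjects within each category". Every summary table carries the population size per treatment group, and all eCRF data and derived variables appear in subject listings.

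**The concern.** Dropout usually accumulates over follow-up, so the visits that inform duration tend to have the most missing data. On observed cases, a late responder rate describes the subjects who stayed. If leaving is related to response, or differs between doses, the persistence of effect and the ranking of doses could be distorted.

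The one required missing-data sensitivity analysis is built for Month 1. The clause covering other analyses is a permission: it names no trigger, endpoint or method. It could therefore seem that the question the trial exists to inform, which dose lasts, is left to whoever remains in follow-up, with any check chosen after the results are known.

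**Working it through.** **1. What the text can establish.** The two documents give the same rule, so there is no contradiction. The alleged gap lies where the public copy has no text. The secondary endpoints are redacted. SAP 2.4 breaks off at the primary-analysis heading and resumes at 2.5, Safety Analysis. Items are not shown in SAP 2.4.1 and 2.4.2, and protocol 9.1.2.4 is redacted directly after its mention of MI. Duration of response stands in the design statements but not in the visible objectives (protocol 2.1 and 2.1.1, SAP 1.2 and 1.2.1). A late-visit responder endpoint is therefore an inference. The sentence listing the MI covariates describes the primary-endpoint model, so it says nothing about models elsewhere.

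**2. The plan's own figure.** Protocol 5.1 gives 3 groups × (60 active + 20 placebo) = 240, as stated, with 60 per dose. No dropout or response rate is visible, so every rate below is an assumption.

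**3. Error of an observed-case rate.** Let r_obs be response among those observed, d the share missing, and r_miss response among the missing.

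- Rate over all treated subjects = (1 − d) × r_obs + d × r_miss
- Observed-case error = d × (r_obs − r_miss)
- BOCF error = −d × r_miss, taking an unchanged baseline score as non-response (the responder definition is redacted)

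Each cell gives observed-case error / BOCF error in percentage points:

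| r_obs | d | r_miss 10% | r_miss 20% | r_miss = r_obs | r_miss 70% |
|---|---|---|---|---|---|
| 30% | 10% | +2 / −1 | +1 / −2 | 0 / −3 | −4 / −7 |
| 30% | 20% | +4 / −2 | +2 / −4 | 0 / −6 | −8 / −14 |
| 50% | 10% | +4 / −1 | +3 / −2 | 0 / −5 | −2 / −7 |
| 50% | 20% | +8 / −2 | +6 / −4 | 0 / −10 | −4 / −14 |

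The observed-case error has no fixed sign. BOCF has the larger error whenever r_miss exceeds r_obs / 2, that is 15% or 25%.

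**4. Effect on a dose comparison.** Take two doses with equal observed rates and 10% versus 20% missing. The gap over all treated subjects is (0.20 − 0.10) × (r_obs − r_miss).

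- r_obs 30%: 2 points (r_miss 10%), 1 (20%), 0 (30%)
- r_obs 50%: 4 points (r_miss 10%), 3 (20%), 0 (50%)

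With 54 and 48 subjects observed, the standard error is √[p(1 − p)(1/54 + 1/48)]:

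- p = 0.30: √(0.21 × 0.03935) = 9.1 points
- p = 0.50: √(0.25 × 0.03935) = 9.9 points

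The largest ratios are 2 / 9.1 = 0.22 and 4 / 9.9 = 0.40.

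**5. What the planned tables allow.** Suppose 50% respond among 54 observed of 60: 27 responders. Counting the 6 missing as non-responders gives 27/60 = 45%; counting them as responders gives 33/60 = 55%. With 48 observed there are 24 responders, and the limits are 24/60 = 40% and 36/60 = 60%. A reader can form these limits from the counts and the population size.

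**The case for a change.** The strongest reply concerns pre-specification. The optional clause is only a permission, and SAP 2.1 and 2.1.2 let supportive analyses be added after approval without an amendment. The tables allow a non-response rate to be rebuilt, but not an estimate that uses earlier scores, and such an estimate can matter. Suppose half the subjects respond early, and later response is 50% in them and 10% in the others. The true late rate is then 0.5 × 0.5 + 0.5 × 0.1 = 30%.

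- If 10% of early responders and 30% of the others leave, the responders seen are 0.5 × 0.9 × 0.5 + 0.5 × 0.7 × 0.1 = 26.0% of all treated. With 80% observed, observed cases give 26.0 / 80 = 32.5%.
- With the dropout reversed, the figures are 22.0% and 27.5%.

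Standardising over the early score returns 30% both times.

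Heavier loss does more. With true rates of 30% versus 5% and every missing subject a non-responder, 20% missing in both arms moves the active–placebo difference from 25.0 to 31.2 points.

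Part of this stands. The clause fixes no trigger, and a pre-stated rule would be tidier. Large dropout strongly tied to response would matter. But the 30% is recovered by construction, because dropout was made to depend only on the score conditioned on. The 31.2 rests on an extreme assumption, and the documents give no sign of such dropout. The pre-specified secondary analysis is fixed in advance as observed cases; repeats would be additional, and SAP 2.1 requires analyses added after approval to be described in the clinical study report. Subject listings keep the earlier scores available.

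**Conclusion.** The concern does not hold. Observed cases is a consistent, pre-specified and common choice for secondary endpoints in a phase 2 study whose sample size is described as enough to explore safety and responder rates (protocol 9.2.3). The primary, where the main efficacy conclusion is drawn, has BOCF with MI as a check and is unaffected. SAP 2.4.2 already permits the BOCF and MI repeats that a stricter plan would require, and the planned output shows loss by visit.

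No wrong result is demonstrated. Under the assumed rates in the dose comparison (observed response 30% or 50%, 10% versus 20% missing, r_miss 10–20% or equal to r_obs), the shift is 0 to 4 points, at most 0.40 of a standard error. The direction is unknown, and BOCF is not reliably the better estimate.

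This conclusion rests on the public text and on assumed rates. It does not show that late missing data will be harmless. It shows that the documents give no ground for calling their handling a defect. A compulsory late-visit sensitivity analysis is a reasonable preference and no more.

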6.1.5 Method of Treatment Assignment

Before starting the study, a randomization list stratified by study center will be generated. When the Investigator has confirmed subject eligibility, the subject will be assigned a study treatment within the Electronic Data Capture (EDC) system.

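### The imputation model for a missing Month 1 ILA score leaves out later ILA scores and names no variables for its MCMC step: a small, cheaply closed gap in a sensitivity analysis

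*SAP*

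**What the plan says.** SAP 2.4.2 uses BOCF for the primary ITT analysis and commits to one missing-data check: "A sensitivity analysis of the primary endpoint will be performed using multiple imputation (MI) for missing values". Repeating an analysis under another method is left to need. Missing ILA scores are modelled by linear regression "with the following covariates included in the imputation model: treatment and non-missing data from earlier visits than Month 1", with five imputed datasets. On the pattern, the SAP says: "It is expected that the pattern of missing data will be monotonic, with slight deviations being corrected by the Markov Chain Monte Carlo (MCMC) method". It gives no variable list for that step. The label on the missingness assumption spells out one mechanism and abbreviates another. I read it as missing at random; that wording is a separate matter.

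Follow-up runs past Month 1. SAP 1.1.1 describes the trial as one "to assess the efficacy, safety, and duration of response of abobotulinumtoxinA", and Protocol 9.1.3 summarizes efficacy at each visit. Under Protocol 6.1.5, "a randomization list stratified by study center will be generated". Center does not appear among the readable covariates.

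The visit schedule, the ILA time points, the responder definition and the primary analysis model cannot be read. The covariate sentence ends without a full stop, so further covariates may have stood there.

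**The concern.** MI under missing at random is only as good as its predictors. A subject who skips Month 1 and attends afterwards has post-treatment ILA scores that bear directly on the missing value, but the stated time limit excludes them. A covariate lost from the end of the sentence would not naturally undo that limit.

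BOCF gives such a subject the baseline score even if later visits show a clear response. MI is the one committed check on that choice, so it should use the data that speak to it. If poor responders are the ones who skip Month 1, a model with weak predictors imputes them much like attenders in the same arm and keeps part of the observed-case bias.

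**Working it through.** The plan gives no figure to reproduce, because its sample-size inputs are redacted. The check has two parts.

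**1. Does the MCMC step already bring in later scores?** With the listed variables only, Month 1 is the last score in the sequence. A subject with earlier data and no Month 1 score then has a monotone pattern, and MCMC has nothing to repair at Month 1. Missing Month 1 is non-monotone only if later visits are in the variable list, and then the list contradicts the stated time limit. The text does not settle which applies.

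**2. What would later scores change?**

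*Design inputs.* Protocol 5.1 has three groups of 60 active and 20 placebo. SAP 2.1.2 pools placebo, giving 3 × 20 = 60. The comparison is 60 versus 60.

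*Assumptions (none is in the documents).* The scale runs from 0 to 4, and response is an improvement of at least one grade. Month 1 correlates 0.3 with baseline and 0.5 to 0.7 with an early post-treatment visit and with a later visit.

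*Variance of the Month 1 score explained within arm.*
- Baseline only: 0.3² = 0.09.
- Baseline plus one post-treatment visit, early or later, at correlation 0.7: (0.3² + 0.7² − 2 × 0.3 × 0.7 × 0.3) / (1 − 0.3²) = 0.454 / 0.91 = 0.50. At correlation 0.5: 0.25 / 0.91 = 0.27.
- Baseline, early and later: 0.40 to 0.66.

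*Two-arm simulation.* It used 1,500 runs, five imputations and linear-regression imputation, then rounding and dichotomizing, with visit correlations of 0.7. Everyone who missed Month 1 had the later score. Missingness in the active arm depended on the later score. BOCF subjects counted as non-responders. Errors are against the full-data risk difference (about 0.44). Each row is a separate set of runs.

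| Missed | ILA predictors | OC bias | MI bias | MI − OC | MI RMSE |
|---|---|---|---|---|---|
| 5% | baseline | +0.0042 | +0.0037 | −0.0005 | 0.0211 |
| 5% | + early | +0.0044 | +0.0015 | −0.0029 | 0.0189 |
| 5% | + early + later | +0.0053 | −0.0006 | −0.0059 | 0.0174 |
| 10% | baseline | +0.0086 | +0.0066 | −0.0020 | 0.0297 |
| 10% | + early | +0.0086 | +0.0023 | −0.0063 | 0.0266 |
| 10% | + early + later | +0.0104 | −0.0024 | −0.0128 | 0.0246 |
| 15% | baseline | +0.0159 | +0.0131 | −0.0028 | 0.0391 |
| 15% | + early | +0.0180 | +0.0086 | −0.0094 | 0.0343 |
| 15% | + early + later | +0.0147 | −0.0053 | −0.0200 | 0.0312 |

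Change in MI bias from baseline only to the full set:
- 5%: 0.0037 + 0.0006 = 0.0043
- 10%: 0.0066 + 0.0024 = 0.0090
- 15%: 0.0131 + 0.0053 = 0.0184

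Change if an early visit is already in the model:
- 5%: 0.0015 + 0.0006 = 0.0021
- 10%: 0.0023 + 0.0024 = 0.0047
- 15%: 0.0086 + 0.0053 = 0.0139

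With 15% missing completely at random, RMSE was 0.035 for baseline-only MI against 0.034 for OC. With an early visit it was 0.030 against 0.035.

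*One-arm simulation, baseline plus later with no early visit.* It used 60 subjects and a 50% true rate. Month 1 was missed by 15% of non-responders and 5% of responders, and all returned later. The baseline correlation was 0.2. This mechanism depends on the Month 1 response itself, which is harder to repair. With later-visit correlation 0.7, the mean rates were OC 52.7, baseline-only MI 52.6 and MI with the later visit 51.7. Bias fell from 52.6 − 50.0 = 2.6 to 51.7 − 50.0 = 1.7 points, and RMSE from 3.4 to 2.5. With correlation 0.85, bias fell from 52.7 − 50.1 = 2.6 to 51.3 − 50.1 = 1.2 points. These are single-arm rates, not treatment differences.

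Center was not simulated.

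**The case against.** Four objections carry weight.

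- **Few subjects are affected.** The SAP expects near-monotone missingness. At 5, 10 and 15% of 60 the count is 3, 6 and 9 per arm, and both simulations let all of them return. Subjects who leave before Month 1 have no later scores to use. This stands and caps the effect.
- **MI may already differ from observed cases.** A reader might infer that MI adds little to an observed-case analysis in general. The documents do not support that, because the ILA schedule is redacted and an early post-treatment rating would make MI usefully different, as the table shows.
- **Center may be in the plan.** A reader might infer that center is discarded. All that can be said is that the readable list does not name it; the sentence may be cut and the primary model is unreadable.
- **MI still does its job against BOCF.** A reader might infer false reassurance. The figures say otherwise. If carried-forward baseline counts as non-response, BOCF in the one-arm case gives 50% × 0.95 = 47.5%, while MI gives 52.6%. They bracket the truth and lie 5.1 points apart. In the two-arm case at 10% missed, MI and BOCF differ by 0.04 to 0.06 under every covariate set. Such a gap shows sensitivity to the missing-data method.

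None of this removes the explicit time limit or supplies the missing MCMC variable list.

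**Conclusion.** The point holds in a limited form. For subjects who miss Month 1 and return, the stated model leaves out informative later scores, and the MCMC wording does not establish that they enter another way. If baseline is the only earlier ILA, MI for these subjects is close to an observed-case analysis; otherwise it is not.

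The size is about 0.01 to 0.02 in risk-difference bias at 10 to 15% missed when baseline is the only earlier score in the current model. It is about 0.005 to 0.014 when an early score is already there, and smaller at 5%. The first range compares with a model that also gains an early visit, so it does not isolate the later one. The one-arm case does isolate it and shows single-arm reductions of 0.9 and 1.4 points. All sizes rest on assumed correlations, an assumed scale and responder rule, and assumed missingness. No size can be given for center.

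The primary analysis is unaffected. Low severity; a cheap improvement.

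**What to change.** Amend SAP 2.4.2 before database lock, as SAP 2.1 provides:

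- State that the imputation model contains treatment and all available ILA scores at maximum contraction, before and after Month 1.
- Either list those variables for the MCMC step already planned or use fully conditional specification. Either one lets a missed-and-returned subject draw on later scores.
- Include study center, with small centers pooled, if the full list does not already have it.
- Keep BOCF as the primary analysis.

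The cost is a few lines of SAP text and a longer variable list, with no new data. The downside is a slightly larger model, which may need center pooling to converge.
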